5.4.1 Use of DataCore/EPIC Information for Recruitment Purposes

This study will utilize EPIC to identify potential participants. A study team member who already has (or will have been given) access to the medical record will screen for eligibility for the study. The PI and approved study staff (e.g., clinical research coordinator) will have access to these search results. During recruitment windows, medical records of patients with scheduled visits at study sites will be reviewed each workday to identify potential participants scheduled for clinic visits the following workday who meet eligibility criteria contained in the medical record. Data points reviewed will include sex, age, menopausal status, breast cancer diagnosis and staging, comorbidities and previous conditions, surgical history, breast cancer treatment history, and medication use.

Once potential subjects have been identified using EPIC, the study team member will notify the treating physician or that physician's nurse practitioner or physician assistant that they have patients potentially eligible to participate. At that point, either of the following will occur:

- Treating physician or that physician's nurse practitioner or physician assistant agrees to permit study team member to contact potential subjects on their behalf, after the clinician obtains verbal consent from the patient to be contacted as a direct approach (see screening procedure in 5.4)
- The study team will mail the IRB-approved patient letter to potential subjects, or email a flyer through MyChart, if they do not have a scheduled medical appointment after referral to our study by a clinician.
- Provide physician or that physician's nurse practitioner or physician assistant with an advertisement to provide to potential subjects

Study staff will work with DataCore to identify patients who may meet inclusion criteria. Specifically, DataCore will conduct a query in Epic to find potentially eligible patients. Data points to be searched in this query will include age, diagnoses, and medication use. The query will be run after IRB approval and as needed during the course of the study, depending on recruitment rates. Query results will be used solely for identification of patients who may be eligible for the study. Using query results, DataCore will set up an IRB-approved contact message in MyChart for distribution. The recruitment message may be repeatedly sent in MyChart up to two times at two-month intervals. Patients who respond in MyChart that they are interested in the study will be contacted by the study team, who will follow the approved recruitment procedures. The study team will discard contact information from patients who do not meet inclusion criteria or who do not wish to participate in the study. If a subject requests information regarding opting out of further recruitment for all research, subjects will be directed to contact [contact] or [name].

Once contact is made, approved recruitment language (see script) will be used to communicate the reason for the contact, and potential participants will be asked if they are interested in participating in this study. Should the potential participant agree, the study team member will screen the participant for eligibility and provide the potential participant with information regarding next steps. Any recruitment information sent by email will utilize Send Safe email. Should a potential participant decide not to participate, reason for non-participation will be recorded and screening forms will be destroyed by shredding.

If a potential subject requests information regarding opting out of further recruitment for all research, she will be directed to email [contact] or call [contact].

CONFIDENTIAL

5.5 Duration of Study Participation

The duration of study participation after informed consent is approximately seven months, which includes the three assessments (i.e., TP0, TP1, TP2) and the intervention between the TP0 and TP1 assessments. The time between initial screening and the enrollment visit (i.e. TP0) will vary depending on the speed with which a sufficient number of potential participants for randomization is recruited. The investigators plan to recruit in each cycle until a sufficient number of potential participants who meet eligibility criteria are recruited, at which point enrollment visits will be scheduled. Investigators will continue these cycles until the target sample size of evaluable participants is reached.

5.6 Total Number of Participants and Sites

Recruitment will end when 40 participants are enrolled. It is expected that approximately 40 participants will be enrolled to produce 32 evaluable participants.

5.7 Participant Withdrawal or Termination

5.7.1 Reasons for Withdrawal or Termination

Participants are free to withdraw from participation in the study at any time on request. An investigator may terminate participation in the study if:

- Any adverse event (AE), laboratory abnormality, or other medical condition or situation occurs such that continued participation in the study would not be in the best interest of the participant.
- The participant meets an exclusion criterion (either newly developed or not previously recognized) that precludes further study participation.
- The participant becomes claustrophobic during an MRI scan.
- The participant sustains a head injury between study visits.
- The participant has an MRI-incompatible metal object implanted between assessment visits (study personnel or an MRI technologist will determine whether any new metal implants will be safe for MRI according to the procedure described in section 5.2).
- The participant fails to attend at least 70% of intervention visits.
- The participant is lost to follow-up.

5.7.2 Handling of Participant Withdrawals or Termination

If a participant cannot be contacted for follow-up using all of the contact information collected, no further efforts will be made to contact the participant and that participant will be considered lost to follow-up. Abrupt termination of participation in the study intervention poses no safety risk to participants. As this study is minimal risk, efforts will not be made to collect safety and efficacy data after withdrawal.

If participants withdraw or are withdrawn from an intervention cycle, additional participants may be added to subsequent cycle(s) to reach recruitment targets for the number of evaluable participants.

Any data and banked specimens collected before withdrawal from the study will be retained for analysis, and no new data will be collected. If the participant requests that data and blood samples be destroyed, all paper records will be shredded, blood samples will be destroyed, and any data already processed into computer files will be removed. However, if results based on the participant's data have been submitted for publication or presentation before the request is made, the results cannot be removed from the publication or presentation.

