7.3.5 Final Study Visit (Visit 13)

TP2 (long-term follow-up assessment within three months [+/- 1.5 weeks] of completion of intervention)

- Confirming that eligibility criteria have not changed since TP1 assessment.
- Collect 15 ml (1 tablespoon) of blood for biobanking.
- Obtain any changes in demographic information, medical history, medication history, and alcohol and tobacco use history.
- Assess for any adverse events, serious adverse events, or unexpected problems.
- Complete patient-reported outcome measures.
- Complete neuropsychological testing.
- Complete study assessment questionnaire.

CONFIDENTIAL

- Complete final REDCap diary.
- Notify participant that aggregate-level results will be available after dissemination of study findings begins.
- Instruct participant to report any subsequent event(s) that the participant, or the participant's physician, believes might reasonably be related to participation in this study.

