7.3.6 Withdrawal Visit

If a participant withdraws or is withdrawn from the study, no further study visits or procedures will be completed.

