8.3 Time Period and Frequency for Event Assessment and Follow-Up

The occurrence of an AE or SAE may come to the attention of study personnel during study visits and interviews of a study participant presenting for medical care, or upon review by a study monitor. All AEs including local and systemic reactions not meeting the criteria for SAEs will be captured. Information to be collected includes event description, time of onset, clinician's assessment of severity, relationship to study intervention (assessed only by those with the training and authority to make a diagnosis), and time of resolution/stabilization of the event. All AEs occurring while on study must be documented appropriately regardless of relationship. All AEs will be followed to adequate resolution.

Any medical condition that is present at the time that the participant is screened will be considered as baseline and not reported as an AE. However, if the study participant's condition deteriorates at any time during the study, it will be recorded as an AE. UPs will be recorded in the data collection system throughout the study.

Changes in the severity of an AE will be documented to allow an assessment of the duration of the event at each level of severity to be performed. AEs characterized as intermittent require documentation of onset and duration of each episode.

The PI will record all reportable events with start dates occurring any time after informed consent is obtained until 7 (for non-serious AEs) or 30 days (for SAEs) after the last day of study participation. At each study visit, the investigator will inquire about the occurrence of AE/SAEs since the last visit. Events will be followed for outcome information until resolution or stabilization.

All unresolved adverse events should be followed by the investigator until the events are resolved, the subject is lost to follow-up, or the adverse event is otherwise explained. At the last scheduled visit, the investigator should instruct each subject to report any subsequent event(s) that the subject, or the subject's personal physician, believes might reasonably be related to participation in this study. The investigator should notify the study sponsor of any death or adverse event occurring at any time after a subject has discontinued or terminated study participation that may reasonably be related to this study.

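### Section 5.7.2 stops safety data collection at withdrawal, while 8.3 and 8.5 require adverse events to be recorded and followed beyond it, with no exception for a reachable woman who leaves

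*Protocol*

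**What the plan says.** Two parts of the protocol give rules for the time after a woman leaves.

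**The withdrawal rules.** Section 5.7.2 gives minimal risk as its reason and says that "efforts will not be made to collect safety and efficacy data after withdrawal". It adds: "Any data and banked specimens collected before withdrawal from the study will be retained for analysis, and no new data will be collected". Section 7.3.6 says: "If a participant withdraws or is withdrawn from the study, no further study visits or procedures will be completed". Both cover women who choose to leave and women whom the investigator terminates. The grounds for termination in 5.7.1 include an adverse event that makes continuing against the woman's interest.

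**The safety rules.** Section 8.3 has the PI record reportable events from consent "until 7 (for non-serious AEs) or 30 days (for SAEs) after the last day of study participation". It also says: "All unresolved adverse events should be followed by the investigator until the events are resolved, the subject is lost to follow-up", or the event is otherwise explained; elsewhere the same section allows follow-up to end at stabilisation. On later events it says: "The investigator should notify the study sponsor of any death or adverse event occurring at any time after a subject has discontinued" or ended participation, where the event may be related to the study. Section 8.5 has every SAE followed until it resolves or is judged chronic or stable.

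**The instruction to the participant.** The final visit (7.3.5) includes this step: "Instruct participant to report any subsequent event(s) that the participant" or her physician thinks may be related to the study. Table A schedules it at TP2 only.

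Sections 5.7.2 and 7.3.6 do not mention 8.3. Sections 8.3 and 8.5 make no exception for withdrawal.

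**The concern.** Staff cannot comply with both sets of rules for a woman who has left and can still be reached. Under 5.7.2 they collect nothing more. Under 8.3 and 8.5 they keep recording for 7 or 30 days and follow any open event to an outcome.

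The case that matters most is a woman terminated because of an adverse event. Her event is the one whose outcome is most worth knowing, and 5.7.2 stops its follow-up on the day she leaves. The consequence reaches the safety reporting: 8.4.1 has cumulative AE data sent to the IRB and NINR each year with conclusions on the balance of risk and benefit. If events in women who leave are not sought, those data can be incomplete in the group where events may have led to leaving.

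**Working it through.** No figure in the plan bears on this point, so the check sets the sections side by side.

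**1. Do the rules cover the same women?** Yes. Sections 5.7.2 and 7.3.6 apply to anyone who withdraws or is withdrawn. Section 8.3 applies to all AEs on study and to reportable events for a fixed time after participation ends. Section 8.5 applies to all SAEs.

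**2. Is a woman who leaves released by one of the exits in 8.3 or 8.5?**

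| Exit | Releases a reachable woman who leaves? |
|---|---|
| Resolved or stabilised (8.3) | Only if the event has in fact reached that state, which someone must find out |
| Otherwise explained (8.3) | Only if an explanation has been established |
| Chronic or stable (8.5, SAEs) | Only after the investigator's judgement, which needs information |
| Lost to follow-up (8.3) | No. Section 5.7.2 keeps this for a woman who cannot be contacted, and 5.7.1 lists it as a separate reason |
| Withdrawal | Not listed in either section |

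**3. A worked case.** A participant sustains a head injury between visits. Section 5.7.1 allows termination for this, and 8.1.1 counts injuries during the study as adverse events. Take the withdrawal date as day 0.

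- Under 8.3, non-serious events starting up to day 7 and serious events starting up to day 30 are recorded, and the injury is followed to an outcome.
- Under 5.7.2, no effort is made and nothing new is collected.
- Under 7.3.6, TP1 and TP2 do not take place if they are still ahead. The TP2 instruction to report later events is then not given on schedule.

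**4. Does another section fill the gap?** Section 13.4 has staff ask permission to collect at least vital status, but only for women who revoke authorization to use their health information. It does not cover AE follow-up or ordinary withdrawal.

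**5. When does the window start?** Section 8.3 counts from the last day of study participation and does not define that day for a woman who leaves. The withdrawal date is the natural reading; on it, the full 7 and 30 days fall after withdrawal, where 5.7.2 allows no collection.

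**6. Can the under-count be sized?** No. It would need a withdrawal rate and an AE rate, and the documents give neither. The allowance of 40 − 32 = 8 women between enrolled and evaluable is not a withdrawal rate, because section 5.4 explains it by unusable imaging data.

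Events before withdrawal are not at issue: 8.3 has the investigator ask at each study visit, and the weekly sessions are numbered visits.

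**The case against.** The best defence is that 5.7.2 is the specific rule for withdrawals and gives its reason. This is a minimal-risk behavioural pilot, and the section says that stopping the intervention abruptly is not a safety hazard. Making no effort can be read as no active pursuit. On that reading, the sentence in 8.3 about telling the sponsor of later events is compatible with 5.7.2, since it is a duty to pass on what becomes known. That much stands. The defence does not cover the ban on new data in 5.7.2 set against the active duty in 8.3 to follow open events. Sections 8.3 and 8.5 were written for the same minimal-risk study, and nothing says which section prevails.

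Three stronger readings are tempting and are not supported.

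- **A reader might infer that 7.3.6 itself forbids safety follow-up.** It ends visits and procedures and does not name safety data. The explicit stop is in 5.7.2.
- **A reader might infer that a woman who leaves has no way to report an event.** Section 8.4.1 has participants encouraged to contact staff at once about AEs, although only for events during participation. Section 8.3 notes that events may also surface through medical care or monitor review. The consent form, the manual of procedures and the data and safety monitoring plan are separate documents, not available here, and may say more. What can be said is that the protocol schedules the instruction about later events at TP2 only.
- **A reader might infer that the window could run out before a poor attender is withdrawn, if it starts at her last attended session.** Termination under the 70% attendance rule is optional, and participation also includes homework and weekly diaries. A missed session therefore does not end participation.

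**Conclusion.** The contradiction is real, is in current text, and should be corrected. Followed as written, 5.7.2 leaves an AE that is open at withdrawal without follow-up and leaves events in the 7- or 30-day window unsought. The cumulative AE data can then under-count events among women who leave. The direction is clear for events that would have been found only by asking; the size cannot be estimated.

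The conclusion rests on two assumptions: that the woman can be reached and has not refused contact, and that the separate documents do not already reconcile the sections. Even if they do, the protocol text needs to agree with them.

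This is a defect in a safety procedure. It does not touch the primary effect sizes, the sample size or the power statement. The stop on efficacy data after withdrawal is a separate question.

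**What to change.** 1. **Sections 5.7.2 and 7.3.6.** Reword along these lines: withdrawal ends study procedures and efficacy data collection, except for safety follow-up under 8.3 and 8.5, unless the participant declines further contact.
2. **Section 8.3.** Define the last day of study participation, for a woman who leaves or is terminated, as the date of withdrawal.
3. **Section 7.3.5 and Table A.** Give the instruction to report later events at withdrawal as well as at TP2.

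The contradiction requires no more than this. A fixed series of contacts, patient-reported outcomes after a woman has stopped, and AE tables by arm are not needed to resolve it; section 10.4.4 plans no formal safety analysis.

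The cost is a few sentences of amendment, brief contact with the women who leave, and consent wording that allows it. Some will decline, so the gap narrows but does not close. Sample size, power and alpha do not change.

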5.7.3 Premature Termination or Suspension of Study

This study may be temporarily suspended or prematurely terminated if there is sufficient reasonable cause. Written notification, documenting the reason for study suspension or termination, will be provided by the suspending or terminating party to the PI and NINR, depending on who suspends or terminates the study. If the study is prematurely terminated or suspended, the PI will promptly inform the IRB and will provide the reason(s) for the termination or suspension.

As this study will evaluate preliminary efficacy, it will not be possible to determine whether the intervention

CONFIDENTIAL

is efficacious or futile for this population during the study. Circumstances that may warrant temporary suspension or termination or include, but are not limited to:

- Determination of unexpected, significant, or unacceptable risk to participants
- Insufficient compliance with protocol requirements
- Data that are not sufficiently complete and/or evaluable with no immediate feasible plan to compensate

If the study is temporarily suspended, the study may resume once concerns about safety, protocol compliance, and/or data quality are addressed and satisfy the sponsor and/or IRB.

6 Behavioral/Social Intervention

6.1 Study Behavioral or Social Intervention(s) Description

The MBSR group will receive manualized training in mindfulness activities including body scans, gentle stretching, yoga, and mindful awareness.⁴⁸ The HEP control, which was developed to serve as an active control to MBSR, will receive manualized health education in physical activity, functional movement, music therapy, and nutrition—without mindfulness instruction.⁵⁶

6.1.1 Administration of Intervention

MBSR will be administered in person by a trained instructor for eight weekly sessions (approximately 2.5 hours each) and a one-day (approximately 7 hours) retreat. Participants will be asked to complete daily 45-minute mindfulness activities on days the group does not meet to reinforce learning. Homework sessions will be accessible via the Internet or by CD, if preferred by a participant. MBSR activities will include walking meditation, gentle yoga, body scan, and instruction in mindfulness.

The HEP active control consists of manualized activities that will be administered by experts in physical activity, functional movement, music therapy, and nutrition using similar modalities for a matched schedule with the same time requirements. As detailed in the HEP manual, physical activity will include moderate-intensity walking and stretching; functional movement will include balance, stability, and agility; music therapy will include music making, song writing, and imagery; and nutrition will include recommended nutritional intake and how to improve participants' current diets.

The groups will be led by trained instructors who are expert community interventionists and who are contracted as consultants with NYU. The group leaders are contracted for work that they routinely do in the community. The consultants are not engaged in the research activities for this protocol (e.g., collecting data, performing recruitment). The PI and study staff approved by the IRB will oversee the protocol-related activities of the groups. In addition, the IRB-approved research study staff will be on-site during the groups to monitor all activities.

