6.1.2 Procedures for Training Interventionists and Monitoring Intervention Fidelity

MBSR instructors have nationally standardized certification requirements, including familiarity with the MBSR manual. HEP instructors are considered experts in the specific health education content to be covered (e.g., nutritionist, physical therapist). Because HEP instructors have no path to certification in the HEP active control condition, the PI will review the specific sections of the HEP intervention manual with each content expert, as appropriate, to establish expectations for intervention fidelity. A study team member who is not blinded to group assignment will record intervention sessions, which will be randomly assessed by that study team member for fidelity to the manualized interventions after each cycle of the study. Specifically, the study team member will review one randomly chosen treatment session from each group (i.e., MBSR, HEP), flag any deviations from the manual, and code any deviations as equivalent or non-equivalent to the intent of the manual. If the total non-equivalent deviations from the manual are greater than 5% of activities, the PI will meet with the interventionist to evaluate the reason for deviation and whether fidelity can be maintained for the next cycle of the study. If it is determined that the interventionist cannot maintain fidelity, a replacement interventionist will be hired.

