7.1 Study Procedures/Evaluations

7.1.1 Study Specific Procedures

After written informed consent, participants will complete the baseline assessment (i.e., TP0) and be randomly assigned to the MBSR or HEP group in a permuted block design stratified by receipt of chemotherapy (i.e., two strata). To reduce bias, research staff who assess participants, as well as the PI, will be blinded to group assignment. At regional community centers, the MBSR group will receive training from a trained instructor during a group-based, approximately 2.5-hour manualized educational activity weekly for eight weeks. Participants will be asked to complete daily 45-minute mindfulness activities on days the group does not meet and a one-day weekend retreat (approximately 7 hours) to reinforce learning. HEP, which was developed to serve as an active control to MBSR, will receive manualized health education, without mindfulness instruction, using similar modalities for a matched schedule with the same time requirements. Participant engagement will be assessed through attendance records, and by percentage of homework completed and mindfulness activities during study participation assessed using REDCap diaries. Assessments will be done at three time points (see Figure – MBSR Study Schema): within three weeks pre-randomization (TP0), within three weeks after completion of the intervention (TP1), and three months (+/- 1.5 weeks) post intervention (TP2). Functional and structural brain imaging will be done at the NYU Center for Brain Imaging at TP0 and TP1. Neuropsychological tests and blood draws will be completed at the Bluestone Center for Clinical Research, Meyers College of Nursing, or New York University Center for Brain Imaging at TP0 and TP2. Neuropsychological tests will not be performed at the post-intervention assessment (i.e., TP1) due to likelihood of practice effects at that interval (i.e., two months). Patient-reported outcomes (see Patient-Reported Outcomes below for detail of these study measures) will be assessed at each time point.

Demographic and Clinical Characteristics. Demographic and clinical characteristics will be collected by patient self-report at TP0 and confirmed, when possible, by medical record review. A list of concomitant medications will be collected from participants at each study visit and confirmed, when possible, by medical record review.

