10.6 Measures to Minimize Bias

10.6.1 Enrollment/Randomization/Masking Procedures

After written informed consent at the enrollment visit, participants will complete the baseline assessment (TP0) and be randomly assigned to the MBSR intervention group or HEP active control group in a permuted block design stratified by receipt of chemotherapy (i.e., two strata). It will not be possible to blind study participants or interventionists to group assignment. However, to reduce bias, research staff who conduct participant assessments (TP0, TP1, TP2), including the PI, will be blinded to group assignment (i.e., single blind). Participants will be reminded not to reveal their group assignment to study staff conducting assessments. The study biostatistician will have no direct contact with study participants and will not be blinded to group assignment. The biostatistician will produce and maintain the randomization codes for the permuted blocks. Randomization may only be unmasked by the biostatistician at the completion of analysis of the primary outcome, or for reporting of SAEs or UPs for which it will be essential to provide information to the PI on group assignment.

As described in section 5.7.2, participants who withdraw or are withdrawn from the study may be replaced with additional participants in the next cycle of the intervention with the intent of obtain at least 32 analyzable participants. For this study of preliminary efficacy, which is determining effect sizes, as large an analyzable sample size as possible will refine the estimates of these effect sizes.

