10.6.2 Evaluation of Success of Blinding

Blinding will be considered successful if, with the exception of SAE and UP reporting, the PI and study staff conducting assessments remain unaware of group assignment until after data collection is complete.

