14.1 Data Collection and Management Responsibilities

Data collection is the responsibility of the clinical trial staff at the site under the supervision of the site PI. The investigator is responsible for ensuring the accuracy, completeness, legibility, and timeliness of the data reported.

All source documents should be completed in a neat, legible manner to ensure accurate interpretation of data. Black ink is required to ensure clarity of reproduced copies. When making changes or corrections, cross out the original entry with a single line, and initial and date the change. **DO NOT ERASE, OVERWRITE, OR USE CORRECTION FLUID OR TAPE ON THE ORIGINAL.**

Copies of the electronic CRF (eCRF) will be provided for use as source documents and maintained for recording data for each participant enrolled in the study. Data reported in the eCRF derived from source documents should be consistent with the source documents, or the discrepancies should be explained and captured in a progress note and maintained in the participant's official electronic study record. Data obtained from paper source documents (e.g., patient-reported outcomes) will be entered twice and compared to reduce potential for data entry error.

Data generated in the study and clinical data entered directly from source documents (e.g., AEs, concomitant medications) will be entered into the SPSS dataset maintained by the PI and approved study staff. The dataset will be password protected and will be examined for data that appear inconsistent, incomplete, or inaccurate.

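### The PI's assigned duties are not reconciled with the PI's declared blind, and the protocol gives that blind two different end points

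*Protocol*

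**What the plan says.** **The blind.** Protocol 7.1.1: "To reduce bias, research staff who assess participants, as well as the PI, will be blinded to group assignment". Protocol 10.6.1 counts the PI as an assessor: "research staff who conduct participant assessments (TP0, TP1, TP2), including the PI, will be blinded to group assignment (i.e., single blind"). The same section concedes that "It will not be possible to blind study participants or interventionists to group assignment", so the blind on the assessing staff and the PI is the only one the trial has.

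**The PI's duties.**
- 6.1.1: "The PI and study staff approved by the IRB will oversee the protocol-related activities of the groups". It adds that approved research staff will be on site to monitor the groups, and does not say that they are different people from the blinded assessors.
- 6.1.2: an unblinded team member records sessions and codes fidelity after each cycle. Where non-equivalent deviations pass a limit of 5%, the consequence is that "the PI will meet with the interventionist to evaluate the reason for deviation and whether fidelity can be maintained". The meeting looks ahead to the following cycle.
- 14.1: study data "will be entered into the SPSS dataset maintained by the PI and approved study staff".

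**The safeguard.** Section 8.8 excludes the PI from monitoring procedures that involve group assignment, names the biostatistician as substitute, and gives the biostatistician all metrics by group. Section 10.6.1 leaves the randomization codes with the biostatistician.

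**When the blind ends.** 10.6.1: "Randomization may only be unmasked by the biostatistician at the completion of analysis of the primary outcome", apart from certain safety reports. 10.6.2 calls blinding successful if, safety reporting aside, the PI and assessing staff "remain unaware of group assignment until after data collection is complete". Section 10.6.3 uses the same earlier end point.

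**The concern.** Participants and interventionists know the arm, so protection against assessment and processing bias rests on the assessors and the PI not knowing it. The protocol assigns the PI tasks that could reveal allocation, and the sections that assign them do not say how the blind is kept. Its success criterion for blinding can also be met before the imaging data, which carry the primary endpoint, have been processed.

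Two things are at stake. One is the conduct of post-randomization assessments by staff who are meant to be blind, in particular the staff-administered neuropsychological tests at three months (TP2). The other is the handling of scans. Section 13.4 sends them to the PI's research offices for pre-processing and analysis, and section 5.4 expects some to be unusable because of head movement or artifacts. Neither 5.4 nor Aim 1 of the SAP gives a threshold for that judgement. The resulting effect sizes are meant to size a later trial (10.2), so it matters that a reader can trust they were produced blind.

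**Working it through.** The blinding question has no figure of its own to recompute. The check sets the provisions side by side.

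**1. Does each duty carry a blinding exception?**

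| Section | PI's duty | Exception in that section | What 8.8 and 10.6.1 add | What stays open |
|---|---|---|---|---|
| 6.1.1 | Oversees the groups' protocol-related activities | None | 8.8 covers monitoring that involves group assignment | Whether group oversight falls under 8.8; whether on-site staff also assess |
| 6.1.2 | Meets an interventionist if deviations exceed 5% | Recording and coding go to an unblinded team member; the meeting does not | Nothing specific | Whether participants are discussed by arm |
| 14.1 | Maintains the dataset with approved staff | None | 10.6.1: codes stay with the biostatistician | Whether attendance and diary fields are in that file |

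On the last row, 6.1.3 records attendance at sessions of either programme, and 10.4.5 summarises minutes of mindfulness activity. Either could indicate the arm if visible for an individual woman.

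**2. Can exposure come before an assessment?** Baseline (TP0) precedes randomization (7.3.2), so only TP1 and TP2 can be affected. By 7.1.1, TP1 falls within three weeks after the intervention and TP2 at three months, plus or minus 1.5 weeks. Fidelity is reviewed after each cycle. A meeting soon after a cycle ends therefore comes before that cycle's TP2 visits and may come before some TP1 visits. Neuropsychological tests are given at TP0 and TP2, MRI at TP0 and TP1.

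**3. Do the two end points coincide?** Data collection ends with the last TP2 visit. Scans move to the PI's offices when ready for processing (13.4), and no date ties that step to the end of data collection. If processing of any scans runs past the last TP2 visit, there is an interval in which 10.6.1 still requires the mask but 10.6.2 would already count blinding as successful. In that interval the PI could learn the arms, in breach of 10.6.1, and the success criterion would not register it.

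**4. Figures that bear on size.**
- Recruitment margin: 40 − 32 = 8, and 8/40 = 20%.
- Stated power in 10.5: 16 per group, effect size 1, two-sided alpha 0.05, equal-variance t-test. With df = 2 × 16 − 2 = 30 and noncentrality = 1 × √(16/2) = 2.828, exact power is 78.14%, which reproduces the stated 78.1%.
- The fix alters none of these inputs, so sample size, power and alpha stay as they are.

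**The case against.** The strongest reply is section 8.8. It shows that the sponsor meant to keep the PI away from anything involving group assignment, and it names a substitute. The codes are with the biostatistician. Section 6.1.1 does not place the PI in the sessions. The fidelity meeting is conditional, concerns adherence to a manual, and need not name any participant. Reviewing the control manual with its instructors reveals nobody's allocation. Section 14.1 does not say that the PI's file holds arm, attendance or diary data. Diaries are also only suggestive, since all participants complete them after the sessions end, partly to detect mindfulness practice in the control group (7.3.4). Participants are reminded not to reveal their group (10.6.1), and accidental unblinding must be reported (10.6.3). On timing, 10.6.1 already forbids unmasking before the primary analysis is complete, and 10.6.2 only says how success is judged.

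Most of this stands, and it rules out the reading that the PI's duties break the trial's only blind. Exposure of the PI would also not by itself unblind the other assessors. What the reply does not do is close the gap. Section 8.8 concerns data and safety monitoring. It does not mention group oversight, fidelity meetings, dataset fields or image processing, and 6.1.1, 6.1.2 and 14.1 do not refer back to it. Nor does the rule in 10.6.1 repair a success criterion that stops earlier.

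**Conclusion.** The concern holds as an unreconciled inconsistency. The PI's blind is left open to being broken, and blinding could be declared successful before image processing is finished. This should be corrected, but it is not evidence that the blind failed.

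The size of any bias cannot be derived from the documents. A reader might infer that the PI decides which scans are evaluable, and so which 32 of 40 women are analysed. No section says so: 13.4 gives the place of processing, not the person who judges scans. Nor are the 8 women in the margin a count of discretionary exclusions, because replacements for withdrawals (5.7.2, 10.6.1) can draw on the same margin.

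The conclusion rests on three assumptions: that overseeing the groups could show who attends which programme, that attendance or diary data could reach the PI's file because nothing says they are withheld, and that some scan processing may follow the last TP2 visit.

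**What to change.** 1. Extend the exclusion in 8.8 to 6.1.1 and 6.1.2. Group oversight, on-site monitoring and fidelity meetings would be done by the unblinded team member already named in 6.1.2, or by other unblinded staff who carry out no assessments.
2. State in 14.1 that arm, attendance and diary fields are kept out of the PI's working dataset and held by the biostatistician until unmasking.
3. Change 10.6.2 and 10.6.3 to match 10.6.1: the PI, assessors and image processors stay blinded until the list of evaluable scans is locked and the primary analysis is complete. The existing exception for safety reporting remains.

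The cost is an amendment to the wording, a small shift of duties to people who are already unblinded, and separate handling of one file. No new staff are needed.
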